This study is minimal risk. The data only phase involves no active participation for patients and will be looking at retrospective data regarding access to usual care and utilization of SUD and depression care prior to the implementation of the systematized screening tool. It would be impractical to obtain informed consent from ~5,000 HIV patients who receive their routine care from one of the three participating KPNC HIV clinics.

Waiver of Signed Informed Consent

Phase 2 (TAPS/AOQ Administration):

Condition 1 applies to our request for waiver of signed informed consent. Prior to and during routine annual HIV clinic visits, HIV patients with a KP.org account will be asked via secure message to complete the questionnaire in KP.org. The secure message will contain the elements of consent as well as a link for participants to click to complete the questionnaire. Clinicians will also have an opportunity to administer the questionnaire on an as needed basis (e.g. if the tablet is unavailable) via suspended hyperspace during the clinical visit. The elements of consent are also reiterated in the instructions displayed at the beginning of the questionnaire to ensure that patients who complete their screening via tablet or suspended hyperspace also review the necessary information and consent is assumed when patients continue to fill out the questionnaire.

after reading the instructions. We are requesting a waiver of written informed consent since it would be impractical to obtain written consent from ~5,000 HIV patients who may receive the survey more than once.

In addition, we originally envisioned that clinic staff would assist with sending surveys and adding in written informed consent to the workflow would be overly burdensome to both providers and their patients. Finally, the research involves no more than minimal risk for participants as these routine, clinically important questions about substance use and mental health are already being asked by their providers in HIV clinics (with no written consent required) during their appointments..

Associates) and all PHI will be removed from transcriptions prior to data analysis. Quantitative measures will also be collected from study participants via online survey hosted by KPNC IT-approved Datstat technology. No PHI will be collected during the online survey and subjects will only be identified by their medical center (OAK, SAC, SF) and their job category (clinician, support staff, BHS, etc.).

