Patients will only be flagged to be asked to complete the questionnaire every 6 months. Clinicians may choose to administer the questionnaire via the suspended hyperspace feature in the interim period if they deem it appropriate follow up for clinical care, however no appointment will be flagged to have a questionnaire directly attached for patient completion prior to their visit if a TAPS/AOQ has been completed within 6 months.

BHS-delivered intervention. Drs. [name] and [name] will meet with clinic BHSs to introduce (or review) core cognitive behavioral therapy (CBT) - and motivational interviewing (MI)-based interventions. BHSs will be trained to review results of all computerized screenings and to provide outreach by phone²¹⁰ and/or web-based patient portal (KP.org) using secure messages. They will be coached on patient engagement and patient-centered goal setting (e.g., noting screening results but also focusing on patients' priorities and concerns), and instructed to offer individual MI/CBT sessions by phone or in person, according to clinical assessment and patient preference. MI and CBT can be effectively combined to address co-occurring depression and substance problems.²¹⁷⁻²¹⁹ BHSs will use MI to enhance motivation to initiate specialty SUD or psychiatry treatment within KPNC for higher severity patients, which is available for all members in facilities nearby to each primary care clinic.

Intervention training. The study team will meet with staff and providers early in the implementation phase to assist with planning for tablet or suspended hyperspace-based administration based on our prior work, e.g., work flow considerations.⁹¹ Orientation for physicians and other providers (e.g., nurse practitioners) will include review of the new screening measures, how to locate scores in the EHR, and the BHS role in patient care and the intervention.

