Overview. The proposed study's primary aims are to examine the implementation and effectiveness and cost of computerized screening and BHS-delivered intervention. In context of the stepped wedge study design, HIV, SUD and depression outcomes will be compared between the intervention and observational phases. We will evaluate both short-term (i.e., within intervention phase) and long-term (i.e., within 1-2 years after initial intervention phase). As described in detail below, we will also employ two complementary study designs: 1) a repeated cross-section design with a different mix of individuals in each cluster (clinic) for examining implementation outcomes (e.g., Aim 1: screening rate) and 2) a cohort design for examining effectiveness in outcomes over time within the same individuals (e.g., Aim 2: retention in HIV care). Finally, we will evaluate implementation cost and cost-effectiveness, and perform qualitative interviews to assess provider- and clinic-level implementation barriers.

General Random Effects Model. Data analysis for both the cross-sectional and cohort approaches will use the random effects modeling framework which accounts for correlation between individuals within clusters and over time and is generalizable to non-normal distributions.¹¹ The general linear model is written as: $Y_{ijk} = m_{ij} + a_i + b_j + QX_{ij} + \epsilon_{ijk}$

where Y_{ijk} denotes the outcome for individual k in cluster i at time j . m_{ij} is the mean for cluster i at time j , a_i is the random effect for cluster i , β_j represent fixed effect corresponding to time j , and X_{ij} is the treatment mode in cluster i at time j . α_i and ϵ_{ijk} are independently distributed with appropriate distributions (e.g., logistic for binary outcomes, normal for continuous outcomes) and individual level covariates (e.g., gender, age, severity) to describe mean responses may be added to this model. The underlying distribution from the model can be linked to a linear predictor by appropriate transformations (e.g. binary outcome linearized using a logit link). These models may be estimated using SAS PROC MIXED or PROC NLMIXED for normal or non-normal distributions allowing for correlation between observations and variable cluster sizes.

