Aim 2. To examine the effectiveness of computerized screening and BHS-delivered intervention in HIV primary care among patients with moderate or high SUD risk or depression severity. We will first compare treatment initiation in specialty clinic for those with severe SUD or depression problems and anti-depression medication prescription rates, among all patients who screen positive (**Aim 2, Hypothesis 1**). The repeated cross-section analyses will be conducted using the random effects (mixed) model framework as above with the dependent variable (whether a patient received any prescription orders initiation with SUD specialty care or Psychiatry treatment for their SUD (depression) being dichotomous. Drawing from preliminary analyses, we will include all patient-level predictors (e.g. demographics such as age and gender, severity) that are likely to be related to these outcomes. These models will use logistic regression since the outcome is dichotomous. We will use the SAS® NL MIXED or similar procedure for analyses. Sample size permitting, we will also examine the use of Buprenorphine/Naloxone for the subset of HIV patients with opioid addiction.^{243,244}

We will also examine the longitudinal (cohort) effect of the intervention on clinical outcomes by comparing changes in HIV clinical parameters (**Aim 2, Hypothesis 2**) and SUD and depression severity (**Aim 2, Hypothesis 3**) for those who have return visits within the study observation period, adjusting for time between visits. We will examine changes in these values between the patient's initial screening and their subsequent visits using the random effects model described above. For example, we expect the coefficient of interest of the time x intervention variable to be positive, which would imply that BHS-delivered intervention results in greater increase in ART adherence.

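### The model said to handle correlation over time has no term linking one patient's records; secondarily, the sustainability test as described cannot show maintenance

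*Protocol*

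**What the plan says.** Under Data Analysis, General Random Effects Model, the protocol adopts one framework for the cross-sectional and cohort approaches. It is described as one that "accounts for correlation between individuals within clusters and over time". The equation is Y_ijk = m_ij + a_i + b_j + Q·X_ij + ε_ijk, for individual k in cluster i at time j. The only random effect is for the clinic. The time terms "represent fixed effect corresponding to time j". The clinic effect and residual are said to be independently distributed. The software sentence adds that the SAS procedures fit such models "allowing for correlation between observations and variable cluster sizes", without naming a structure.

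On who is analysed, the Data Analysis Overview describes Aim 1 as a repeated cross-section with "a different mix of individuals in each cluster" and Aim 2 as "a cohort design for examining effectiveness in outcomes over time within the same individuals". Study Procedures, Phase 2, says: "Patients will only be flagged to be asked to complete the questionnaire every 6 months". The request for a waiver of signed consent speaks of "HIV patients who may receive the survey more than once". The Aim 2 analysis examines change between each patient's "initial screening and their subsequent visits using the random effects model described above", and its coefficient of interest is time by intervention.

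On sustainability, the Aim 1 analysis compares outcomes in the first and second year of the intervention. It lets a one-sided test of the time coefficient indicate whether they held up in year 2.

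**The concern.** Under the equation, two records of one patient are no more alike than records of two different patients in the same clinic. Aim 2 is by design about the same individuals. In Aim 1 a different mix does not mean separate samples: the same three registry clinics are followed throughout and patients are asked again after 6 months. The property claimed for the framework is therefore absent from the model that is written.

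At stake are the standard errors. Repeated records are counted as independent information on covariates that vary mainly between patients, such as age and HIV severity (Aim 1 Hypothesis 2). Several changes measured from one baseline share that baseline, so they are correlated by construction.

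The secondary point concerns the part of Aim 1 Hypothesis 1 that expects outcomes to be maintained long-term. The model has a set of period effects and no single time coefficient. Starts are staggered, so calendar period and time since a clinic's own start differ. A one-sided test against zero does not test maintenance in either direction.

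**Working it through.** The protocol states no correlation, recurrence rate, alpha or margin, so there is no figure of its own to reproduce. What follows is illustration under stated assumptions.

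**Inputs.** From the protocol: 4 repeated measures per clinic (Aim 1 analysis); 4,600 patients in 3 clinics (HIV registry), so 4,600/3 ≈ 1,533 per clinic. Assumed: patient correlation ρ = 0.3, 0.5, 0.7; share r of the other 3 periods in which a patient also has a record, 0.4 unless stated.

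**1. Patient-level covariates, linear scale.** For a covariate fixed within patient (age), model SE over true SE = 1/√(1 + 3rρ), and type I error = 2·P(Z > 1.96 × ratio).

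| ρ | 1 + 3(0.4)ρ | SE ratio | Type I error |
|---|---|---|---|
| 0.3 | 1.36 | 0.857 | 9.3% |
| 0.5 | 1.60 | 0.791 | 12.1% |
| 0.7 | 1.84 | 0.737 | 14.8% |

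- Other recurrence rates: r = 0.2 gives 7.1-10.0%. If every patient has a record in all 4 periods, it is 15.5-26.6%.
- CD4-like covariate with assumed period-to-period correlation 0.8: replacing 3rρ by 3rρ × 0.8 gives 1.288, 1.480 and 1.672, hence 8.4%, 10.7% and 13.0% at r = 0.4.
- Screening is binary. A logit simulation (3 clinics, 4 periods, 400 patients per clinic and period, latent ρ as above, r = 0.4) gave 7.6%, 9.4% and 11.8% for age, so the linear figures are somewhat high for that outcome.

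**2. Aim 2, changes from initial screening.** With exchangeable correlation each change has variance 2σ²(1 − ρ), and two changes of one patient correlate 0.5 whatever ρ is. Take follow-up visits t = 1, ..., m and two groups, analysed as if changes were independent.

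- Slopes from baseline: SE ratio = √[Σt² / (0.5Σt² + 0.5(Σt)²)]. For m = 2: √(5/7) = 0.85, type I error 9.8%. For m = 3: √(14/25) = 0.75, type I error 14.2%.
- Intervention main effect included, so the time term is a within-patient contrast: SE ratio = √(1/0.5) = 1.41, too large, with loss of power.
- m = 1: ratio 1, no error.

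**3. Aim 1 intervention effect.** SE ratio = 1/√(1 − rρ + nw), where n is patients per clinic and period and w is clinic-by-period variance over patient variance. With w = 0 and r = 0.4 it is 1/√0.88 = 1.07 to 1/√0.72 = 1.18, too large. It reverses at w = rρ/n: 0.12/400 = 0.03% to 0.28/400 = 0.07% at n = 400. So small a variance cannot be ruled in or out from the protocol, and no direction follows.

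**4. Sustainability.** Assume one-sided 5%, independent years and a true fall from 40% to 35%. SE = √[(0.40·0.60 + 0.35·0.65)/n] = √(0.4675/n). If the alternative is a fall, the chance of missing it is Φ(1.645 − 0.05/SE).

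| n per year | SE | Missed |
|---|---|---|
| 300 (assumed screen-positive subset) | 0.0395 | 65% |
| 1,533 | 0.0175 | 11% |
| 4,600 | 0.0101 | under 0.1% |

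If the alternative is a rise, a perfectly maintained rate passes only at the test's alpha, about 5%.

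**The case against.** The strongest reply is that the equation is a template. It is called general, covariates may be added to it, and it lacks the time by intervention term that the Aim 2 analysis names. The stated intent is to handle correlation over time, and covariance structure is often left to the SAP, which is not at hand. This stands to the extent that missing detail alone would be no finding. But the protocol writes a model, credits it with a property it lacks, and then refers back to it for within-patient change. The covariates that may be added describe means, not correlation. The general phrase about correlated observations is already met by the clinic effect.

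It is also fair that the sizes rest on assumed inputs, and that the effect is nil or unsigned in places. A reader might infer that every test in the trial is inflated. The working does not support that: the direction is consistent only for patient-level covariates.

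On sustainability, a reader might infer that time is undefined, or that the protocol counts a non-significant fall as success. Neither is supported. The contrast of the first and second intervention year is named, and no null, direction or decision rule is written; counting a non-significant fall as success is one permitted reading. Margin and alpha could also be set in the SAP. What remains is that the one-sided test is offered as the indicator of maintenance and is not tied to a term in the model. With all 4,600 patients the practical risk is small; it is material in smaller subsets.

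**Conclusion.** The main point holds. The model written for both analyses does not deliver the correlation over time claimed for it, and the same patients recur.

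- **Patient-level covariates (Aim 1 Hypothesis 2):** too liberal, about 9-15% for age on the linear scale at 40% recurrence and ρ of 0.3-0.7.
- **Aim 2 time by intervention:** wrong standard error when a patient contributes more than one follow-up change, from 0.75 to 1.41 times the true value in the codings tried; no error with a single change.
- **Aim 1 intervention test:** no direction claimed.

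The Aim 2 figures also assume exchangeable correlation.

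The sustainability point is secondary. Tested against zero, the verdict would depend on the number of patients analysed rather than on how large a fall matters. The miss rates assume a 40% starting rate and treat the two years as independent samples.

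This should be corrected, but it does not undermine the design.

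**What to change.** **Model.** Add a patient random intercept within clinic to the general model. For binary outcomes, state whether this intercept is used or a marginal model with patient-level working correlation and clinic indicators. For Aim 2, either allow correlation among one patient's changes or analyse levels with a patient intercept. The intercept is then essential: levels without it overstate the SE by 1/√(1 − ρ), which is 1.20 to 1.83 for ρ of 0.3-0.7.

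**Sustainability.** Define the term as an indicator for the second year since each clinic's own start, fitted alongside the period effects. Report its confidence interval, and call an outcome sustained only if the lower limit lies above a pre-stated margin.

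**Cost.** No new data are needed. Intervals for patient-level covariates widen, and a choice between patient-specific and population-averaged odds ratios must be made. The year-2 term rests on at most three clinics. One margin must be chosen. For scale, n per year = (1.645 + 0.842)² × 2p(1 − p)/margin². At a true rate of 40% in both years, one-sided 5% and 80% power, a 10-point margin needs about 297 independent patients per year and a 5-point margin about 1,188, before allowing for clustering or for patients present in both years.

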Observational phase: The 12 months prior to implementation at each study clinic will be considered the observational phase consisting of usual care with access to specialty clinic-based SUD and depression care. Hazardous drinking screening has been implemented systematically using NIAAA guidelines,¹⁶⁹ along with standardized tobacco screening; both are part of the clinical workflow in the health system and are captured in the “MA Rooming Tool” used by medical assistants to capture essential preventive health measures. Screening for other substances is not standardized and instead relies on physicians’ clinical practices. A combination of appointment codes and appropriate *International Classification of Diseases, (ICD) 9th and 10th edition* will be used to determine screening for alcohol and drug use. Drug use and depression data are captured in the Social History section of KP Health Connect, and will be extracted from the EHR. Treatments provided to depression patients are based on current best practices for medication management and psychotherapy.^{229,230} Mild to moderate depression is often addressed in primary care with antidepressant medication, whereas patients with more severe symptoms or complex presentations are usually referred to psychiatry clinics for specialty care. We will track these aspects of patient care in the EHR.

Sleep subanalysis: We will be doing additional analysis on sleep disorders related to mental health and substance use that will require the following data: 1) patient reported outcomes on sleep, and 2) ICD9/10 codes for sleep disorders

Phase 2: TAPS/AOQ Administration

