KPNC EHR. The EHR databases links information using unique member identifiers from multiple data sources including demographics, membership, ambulatory, inpatient, laboratory and prescription data. Unit costs of services obtained for each patient encounter and service are also available and can be calculated by member over time, or aggregated to physician or facility level. Vital status is captured comprehensively from member proxy reporting, deaths during a KP hospitalization, regional cancer registry vital status, quarterly Social Security Administration vital status files and death certificates. Additional detail on all EHR data sources is provided in KPNC Resources. After implementation of the intervention, results of KP.org-, tablet-, and suspended hyperspace-based SUD and depression screening during routine primary care visits will be added to the EHR. **HIV registry.** The HIV registry includes all HIV patients since the early 1980s, with HIV-infection confirmed by chart review. It maintains up-to-date lists of all HIV patients, HIV transmission risk factors, dates of known HIV infection, AIDS diagnoses, and complete HIV-related lab and pharmacy data. A total of 8,186 HIV patients are current KPNC members, including 4,600 (56% of all KPNC HIV patients) from the three study clinics.

Study Measures. We will include relevant patient demographic factors in all analyses, including age, sex, race/ethnicity, and HIV risk group. Evaluating these demographics in the context of an insured population allow for the evaluation of potential disparities in screening and treatment rates, independent of differences in access to care. Other study measures for each study Aim are described below.

Aim 1 measures (implementation)

- **SUD and depression screening** during the observational phase will include EHR-based provider-documented screening for SUDs and depression. Intervention phase screening will include provider-documented screening and KP.org-, tablet-, and suspended hyperspace-based screens, also in the EHR.
- **BHS-delivered intervention** during the observational and intervention phases will be defined as one or more in-person or phone visits with a BHS. We will also measure the number of phone and in-person visits.

Aim 2 measures (effectiveness)

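### Aim 2 Hypothesis 1 compares phases among patients whose screen-positive or severe status is ascertained differently in each phase, and Hypothesis 3 measures TAPS change from a score-selected start with no possible usual-care comparator

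*Protocol*

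**What the plan says.** The hypotheses at the start of the protocol set Aim 2 Hypothesis 1 as a contrast of the intervention phase with the observation phase. The Aim 2 paragraph of Data Analysis then fixes the groups. Prescribing is analysed as "anti-depression medication prescription rates, among all patients who screen positive", and the other outcome is "treatment initiation in specialty clinic for those with severe SUD or depression problems". Severity is among the covariates.

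The only definition of screening by phase stands under Study Measures, Aim 1 measures:

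- Before implementation, the measure "during the observational phase will include EHR-based provider-documented screening for SUDs and depression"; no computerized screen is listed there.
- After implementation, the list is wider: "Intervention phase screening will include provider-documented screening and KP.org-, tablet-, and suspended hyperspace-based screens".

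On usual care, the Observational phase text under Study Procedures says that appointment and ICD codes "will be used to determine screening for alcohol and drug use". It also says "Screening for other substances is not standardized and instead relies on" individual physicians. The same paragraph states that hazardous drinking and tobacco were already screened systematically. Aim 1 Hypothesis 1 predicts higher screening rates after implementation.

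Aim 2 as a whole is limited to patients with moderate or high SUD risk or depression severity. The cohort part (Hypotheses 2 and 3) is "for those who have return visits within the study observation period, adjusting for time between visits", with change taken between the "initial screening and their subsequent visits using the random effects model described above".

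**The concern.** The intervention includes a new way of finding cases, and the Hypothesis 1 denominator consists of the cases found. If usual care recognises a selected part of the true positives and the computerized screens add the rest, the treated proportion among positives can move although nobody's chance of treatment has changed. A real gain can be hidden in the same way. Adjusting for severity does not repair this as written: the SUD severity measure named under Aim 2 measures is the TAPS level, which begins with Phase 2.

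Hypothesis 3 has a different problem. Patients who enter because a score is high will on average score lower next time without any treatment effect. Only a group selected by the same score and measured again under usual care would show how much of the fall is of this kind.

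**Working it through.** The protocol gives no screening coverage, treatment rates, score distributions or effect sizes, so there is no figure of its own to reproduce. The only document input below is the 4,600 patients of the three clinics. Everything else is assumed, and the results show what is possible, not what is expected.

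**Hypothesis 1, simple mix.** Assume 920 true positives (20% of 4,600), of whom 690 are known in usual care and 230 are found only by the new screens. Treatment is the same in both phases, with no severity adjustment.

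- Known cases treated 40%, new cases 10%: 0.40 × 690 = 276 and 0.10 × 230 = 23. The rate among positives goes from 40.0% to 299/920 = 32.5%. Over all patients it is 299/4,600 = 6.5% in each phase.
- Known cases treated 20%, new cases 40%: 0.20 × 690 = 138 and 0.40 × 230 = 92. The rate goes from 20.0% to 230/920 = 25.0%. Over all patients it is 230/4,600 = 5.0% in each phase.

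The shift can go either way, and it vanishes when the denominator does not depend on screening.

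**Hypothesis 1, adjusted for true severity** (generous to the plan, which has no common severity measure). Simulation of 400,000 patients, geometric mean over six seeds:

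- A true positive has standard-normal severity above 0.84; u is an unmeasured normal factor.
- Logit of treatment = −1.5 + 0.6 × severity + u, identical in both phases.
- Logit of usual-care recognition = 0.5 × (severity − 1.4) + b × u, which recognises about 50%.
- The observation phase contains the recognised positives. The intervention phase contains all positives or, in a second run, the recognised plus random additions up to 80%.
- The fitted model is logistic on phase and severity. The true phase odds ratio is 1.

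Results over b from 1 to −1:

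| SD of u | Intervention-phase capture | Phase odds ratio under no effect |
|---|---|---|
| 0.5 | 100% | 0.90 to 1.12 |
| 1 | 100% | 0.72 to 1.44 |
| 1 | 80% | 0.78 to 1.32 |
| 1.5 | 100% | 0.57 to 1.91 |

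At b = 0, where recognition is unrelated to treatment given severity, the odds ratio is 1.00. Values above 1 need usual care to recognise the patients less likely to be treated. For severe cases only (severity above 1.4), SD 1 and full capture, the range is 0.74 to 1.38.

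**Hypothesis 3, regression to the mean.** With zero effect, entry at PHQ-9 of 10 or more and a bivariate normal model, the expected fall is (1 − r) × SD × φ(z)/(1 − Φ(z)), with z = (10 − mean)/SD.

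- Mean 5, SD 5: z = 1 and φ/(1 − Φ) = 0.242/0.159 = 1.525. The fall is 0.5 × 5 × 1.525 = 3.8 points at r = 0.5 and 0.2 × 5 × 1.525 = 1.5 at r = 0.8.
- Over mean 4 to 7, SD 4 to 6 and r 0.5 to 0.8, the lowest fall is 1.1 (mean 7, SD 4, r = 0.8) and the highest 4.6 (mean 4, SD 6, r = 0.5).

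The normal model is rough. It puts 16% of patients below zero at mean 5, SD 5, and 25% in the cell that gives 4.6.

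**The case against.** Several points on the other side stand and limit the finding.

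- **Alcohol and tobacco** were already screened systematically in usual care, so the ascertainment gap is clearest for other drugs.
- **Depression.** A reader might infer that usual care held hardly any PHQ-9 scores. The protocol does not support that: Study Procedures describes the AOQ, which contains the PHQ-9, as routinely sent to patients and as standard care throughout KPNC. It does not state coverage in the three study clinics before implementation, so the gap for antidepressant prescribing is plausible but less certain.
- **Size.** Completion is voluntary, so 100% capture is an extreme case. At 80% capture the SD 1 range narrows to 0.78 to 1.32; with usual-care recognition of about 62% against 80% it is about 0.86 to 1.18.
- **Intended comparison.** It would be wrong to say that no phase comparison is meant for symptoms. The Data Analysis Overview announces one, and the Aim 2 paragraph names a time-by-intervention term, illustrated with ART adherence. Neither describes an observation-phase group selected by the same score and measured again. The Hypothesis 3 sentence restricts only to return visits; the score selection comes from the Aim 2 population.
- **Retention.** A reader might also infer that the return-visit restriction removes any gain in retention. That rests on applying to a 12-month visit count a sentence about change between visits. It is one reading, and a clarification is enough.
- **The unseen SAP** may define screen-positive more closely. The denominator and the time origin, however, are fixed in the protocol text.

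**Conclusion.** The point holds in this form and should be fixed; confidence is medium. Followed as written, Hypothesis 1 compares groups that are likely to differ in composition for reasons other than treatment, with no common severity measure to adjust by. This can create or hide a phase difference. The direction is unknown, and there is no bias if usual-care recognition is unrelated to treatment given severity. The documents do not support a claim that the result will favour, or work against, the intervention, and they give no basis for a definite size.

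For Hypothesis 3 the conclusion is firm for TAPS, which has no observation-phase values: a fall among patients selected for moderate or high scores cannot be told apart from regression to the mean. For PHQ-9 it is conditional on whether a same-score, re-measured usual-care group is used. The fall of 1.1 to 4.6 points under zero effect rests on the assumed distribution and correlations.

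**What to change.** 1. **Hypothesis 1.** Define an at-risk group in the same way in both phases, for example by diagnosis codes recorded in look-backs of equal length before the observation phase and before implementation. Base the between-phase conclusion on it. Support it with an analysis of all registry patients who meet one appointment rule in both phases (the present rule is stated for Phase 2 only), without screening-derived severity in the model. Keep the screen-positive comparison, and state the ascertainment difference as a limit on its interpretation. Dropping it in favour of all clinic patients would change the Aim 2 question and is not needed.
2. **Hypothesis 3.** Report TAPS change as uncontrolled and subject to regression to the mean. Do the same for PHQ-9 unless observation-phase patients selected by the same score, with repeat scores, serve as comparator. Also show scores for all screened patients.
3. **Retention.** State that the return-visit restriction does not apply to this outcome.

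The cost is some added analysis of EHR and registry data, with no new patient contact. The all-patient analysis dilutes the effect: a 10-point gain among an assumed 10% to 30% positive appears as 10 × 0.10 = 1 to 10 × 0.30 = 3 points. In a code-defined group of whom an assumed 40% to 80% belong to the target it appears as 4 to 8 points, but that group misses cases found only by the new screening. A PHQ-9 comparator may be small.
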